#### 6.4.4 Vital Signs, Physical Examinations, and Other Assessments

The ECOG PS will be assessed at Screening and at subsequent visits as indicated in the Schedules of Assessments (**Tables 1-3**) and documented in the eCRF (Prometheus).

Body weight will be measured at Screening and at subsequent visits as indicated in the Schedules of Assessments (**Tables 1-3**) and documented in the eCRF (Prometheus). Body height will be measured at screening only.

A physical examination will be conducted at Screening and at subsequent visits as indicated in the Schedules of Assessments (**Tables 1-3**) and documented in the eCRF (detailed description in Section 6.1). Any abnormalities arising or worsening after the signing of the ICF should be

documented in the eCRF (Prometheus) Adverse Event section (see Section 6.4.1). Abnormal findings are to be reassessed at subsequent visits.

Physical examination should include a dermatological examination. If abnormal skin findings are observed, the patient should be referred to a dermatologist for biopsy of suspicious lesions.

An ophthalmology examination including slit lamp evaluation inclusive of the anterior segment and with visual acuity should be conducted at Screening. At subsequent visits, eye signs and symptoms should be checked. If there are any clinically relevant findings then an appropriate ophthalmology examination including slit lamp evaluation inclusive of the anterior segment and with visual acuity should be obtained within 2 days.

Digital 12-lead EKGs will be recorded as a single recording at the screening visit. Subsequent EKGs will likewise be obtained as single recordings.

All newly diagnosed or worsening conditions, signs and symptoms observed since Screening, whether related to trial treatment or not, are to be reported as AEs.

For female subjects of childbearing potential, serum  $\beta$ -HCG pregnancy test will be carried out during the Screening phase. A urine  $\beta$ -HCG test may be performed prior to schedule on treatment assessments. Results of the most recent pregnancy test should be available prior to the next dosing of IMP. Subjects who are postmenopausal (age-related amenorrhea  $\geq 12$  consecutive months and if needed FSH > 40 mIU/mL [in the postmenopausal range] as outlined in Section 6.1.1), or who have undergone hysterectomy or bilateral oophorectomy are exempt from pregnancy testing. If necessary to confirm postmenopausal status, an FSH will be drawn at Screening.

## 6.4.5 Biomarkers

Due to limited understanding of the biological activities induced by M7824 in cancer subjects, there can be no certainty that the doses examined will be associated with relevant antitumor immune activities. Further details regarding translational studies are listed in Appendix 3. As the consequence, the trial will serve to

- 1. Evaluate MSI-H status with CMS subtype
  - a. MSI will be assessed by MSI-H CRC either by IHC for loss of protein expression in one of 4 mismatch repair proteins (MLH1, MSH2, MSH6, PMS2) or by detection of microsatellites within the tumor DNA (as per institutional practices)
  - b. External MSI testing in a CLIA certified laboratory with a documentation of MSI-H status performed prior to screening is acceptable for inclusion in cohort A- C.
- 2. Evaluate PD-L1 expression as a predictor of response
  - a. Primary tumor will be stained for PD-L1 expression by IHC
  - b. PD-L1 staining will be semi-quantitatively scored by absence, weak, moderate, strong by a pathologist

- c. The above will be performed on the mandatory fresh on-treatment biopsy.
- 3. Evaluate the effect on TGF $\beta$  concentrations in plasma.
- 4. Evaluate potential predictive / prognostic biomarker candidates related to the drug and / or the cancer (such as the CMS, immune infiltrating populations, systemic cytokine profiles)
  - a. CMS will be assessed using a 75 gene FFPE based assay using the Nanostring technology in a CLIA-certified laboratory at MD Anderson.
    - i. Current discovery of 74 samples run in 18 batches with random duplicate samples to assess technical validity demonstrate accuracies compared to gold standard gene expression by Affymetrix hybridization:
      - 1. A 75 gene model had 4 group CMS accuracy of 87.1% with very high accuracies (>90%) in CMS1 and CMS2 groups which were over-represented in this small cohort
      - 2. The CMS4 versus other subgroups demonstrated accuracy of 90.6%
      - 3. The Nanostring technology on FFPE has been successfully applied to breast cancer and lymphoma cohorts
      - 4. The Nanostring codesets utilized for the CMS classification are now being assessed for technical validity in MDA's CLIA molecular pathology laboratory
  - b. Immune infiltrating populations will be analyzed by immunohistochemistry (IHC), and Multiplex IF analyses.
    - IHC markers will include, but are not limited to, PD-L1, CD3, Foxp3, CD25, CD8, CD68, CD56, CD20, CD45RO and granzyme B. We may also include PD-L2, B7-H3, B7-x/H4, galectin 9, HVEM and CD48 to measure in tumors and PD-1, 2B4, LAG-3, Tim-3 and BTLA in TILs. These studies will be conducted at TMP-IL.
    - 2. Multiplex IF Analysis. Up to 10 immune markers, 2 panels may be utilized. Currently, there are 2 Vectra panels optimized: Panel#1, CD3, CD8, CD68, PD-L1, PD-1 pan-cytokeratin and DAPI; Panel #2, CD20, CD45RO, FOXP3, Granzyme B, CD57, pan-cytokeratin and DAPI. A third myeloid panel will be developed. For multiplex IF analysis, we will use the Opal chemistry and multispectral microscopy Vectra system (Perkin-Elmer) which includes the Nuance software; analysis will be performed using the InForm software. Additional markers will be selected according the results of the gene expression analysis and may include other

immunotherapy targets (e.g., OX-40, Vista, GITR, TIM-3, LAG-3, NKp46/CD16, etc.) and proliferation markers (e.g., Ki67).

- 3. RNAscope. TGF- $\beta$  and other additional markers may be analyzed by RNA scope.
- c. Immune infiltrating populations and systemic cytokine profiles

i. Blood collections and biopsies prior to week 8 treatment will be collected for immune studies under the supervision of the Translational Molecular Pathology Immunoprofiling Lab (TMP-IL) at MD Anderson.

ii. In tumor tissue, IHC studies will be performed to evaluate  $CD3^+$ ,  $CD4^+$  and  $CD8^+$  T cells,  $T_{reg}$ , NK cells, macrophage [M1/2 profile] infiltrating populations. Fresh tissue will be available for flow cytometry analysis on larger tumor samples only. We will assess the proportion of MDSC, macrophage, DC and NK cell subsets within the Live CD45+ cells in panel 3. The expression of checkpoint ligands will be explored using panel 4. Live cells will be sub-gated as CD45-negative to exclude immune cells. EPCAM will be used as a marker of tumor cells and CD90 as a fibroblast marker. The expression of CD80, CD86, GITR-L, ICOS-L, MIC A/B, B7-H3, B7-H4, CD73, PD-L2, OX40L and other relevant immune cells will be assessed.

iii. In peripheral blood, evaluation by circulating immune populations will include, but not be limited to,  $CD4^+$ ,  $CD8^+$ , NK,  $T_{reg}$ , monocytes and neutrophils as outlined by the Schedules of Assessments (**Tables 1-3**). High order flow cytometry panels will be designed. The panels will focus on 1) delineation of major immune cell types (T cells, B cells, NK cells, DC), 2) determination of T cell differentiation status and limited functionality (IFN $\gamma$ , TNF $\alpha$ , GB) and 3) defining the expression level of costimulatory and coinhibitory molecules on T cells. The proposed studies will be conducted retrospectively on cryopreserved PBMCs.

iv. Serum Cytokine Analyses. Cytokines (IFN- $\gamma$ , IL-1 $\alpha$ , IL-2, IL-4, IL-5, IL-8, IL-10, IL-12p70, IL-13, and TNF- $\alpha$ ) will be measured in the serum using the Meso Scale Discovery Platform (Rockville, MD). This technology allows for the detection of up to 40 analytes per well and uses a very low sample volume. This method has a sensitivity up to 1000 fold higher than traditional ELISA assays with a large linear range of 3-4 logs. The instrument performs immunoassays utilizing electrochemiluminescense to detect the signal in a 96 well plate format. This technology can be utilized for either single agent detection or in multiplex format. A wide menu of validated single or multiplex kits for the detection of 1 to 40 analytes are available from the manufacturer and can be customized.

d. Mutational profiling

- i. KRAS, NRAS and BRAF will be assessed via next generation sequencing in a panel of 409 genes that sequences known hotspots to a coverage of at least x250 coverage depth performed in the Molecular Diagnostic Laboratory (MDL) at MD Anderson. The lab is CAP accredited and CLIA certified to perform high complexity molecular testing for clinical purposes.
- ii. Tumor DNA analysis for KRAS, NRAS and BRAF performed in another CLIA certified molecular diagnostics laboratory do not need to be tested again
- iii. TGF $\beta$  signaling pathway mutations will also be assessed via this panel which will include, but not limited to, TGF $\beta$ R2, ACVR2A, SMAD2 and SMAD4.
- iv. RNA-seq and WES. This analysis will be performed using fresh frozen tissue specimens from CNB at MD Anderson Sequencing Facilities.
- v. Optionally, using plasma specimens, genotyping analysis of circulating free DNA (cfDNA), circulating tumor cells (CTCs), and exosome (exo)-DNA may be performed to monitor tumor response and progression.
- 5. Microbiome analyses of buccal and fecal biospecimens
  - i. Buccal and fecal specimens may be collected at defined time points for microbiome studies. Buccal swab (buccal smear or cheek swab) will be collected firmly rubbing the entire inner surface of both cheeks for 10 sec each side using a sterile polyester swab using standard SOPs. Stools for enteric microbiome analysis will be collected using the OMNIgene kit (DNA Genotek, Ottawa, Ontario, Canada). The collection will allow obtaining high quality DNA suitable for microbiome profiling and sequencing.
  - ii. Analysis: Bacterial identification and classification is achieved by profiling the 16S rRNA gene, which is present in all bacteria but has sufficient sequence level diversity for classification purposes. 16S deep sequencing is cost-effective and technically and computationally robust, and can be utilized as a primary assay to initially characterize fecal samples. Briefly, the bacterial 16S rRNA V3-V4 region from each sample will be amplified and amplicons sequenced using a MiSeq 2x250 bps protocol. An internal pipeline will be utilized for read processing and analysis. Operational taxonomic unit (OTU) classification will be achieved by mapping the UPARSE OTU table to an optimized version of the SILVA database. Abundances will be recovered by mapping the de-multiplexed reads to the UPARSE OTUs and a custom script will construct an OTU table from the output files generated in the previous two steps. This OTU table will be used to calculate diversity, 2-dimensional visualization, and taxonomic summaries.

Details of time points and sampling are provided in the Schedules of Assessments (Tables 1-3).

All proposed biomarker analyses are exploratory and dependent on the quality and availability of sufficient materials. The panel of biomarkers might be adjusted based on results from ongoing research related to anti-PD-1 / PD-L1 therapies and / or safety, therefore, each subject will also be asked whether any remaining tumor tissue and blood-derived samples can be stored at a central repository (until such time as these samples cannot support any further analysis) and can be used for future exploratory research on the drug and / or disease-related aspects. A subject's consent to the use of any remaining samples for such future exploratory research shall be optional and shall not affect the subject's participation in the current trial.

## 6.4.5.1 Target-related Biomarkers

Blood will be collected to analyze PD-L1 target occupancy, TGF $\beta$  1, 2, 3 concentrations, and circulating cytokine levels according to the Schedule of Assessments (**Tables 1-3**).

## 6.4.5.2 Immunomonitoring

As biomarker research is constantly evolving, the selection of markers with the highest specificity and relevance to treatment effect may change.

Leukocyte subpopulations and immune activation status will be assessed by flow cytometry (fluorescence-activated cell sorter [FACS]) on PBMC from heparinized blood samples (10 mL, tubes) drawn at the time points outlined in the Schedule of Assessments (**Tables 1-3**).

Soluble factors (for example, cytokines profile, soluble PD-1, and soluble PD-L1) will be assessed on blood (plasma / serum) samples collected as outlined in the Schedule of Assessments (**Tables 1-3**).

Plasma will be stored at -80 degrees and sent for immunoprofiling for interleukin (IL) IL-1 $\alpha$ , IL-1 $\beta$ , IL-2, IL-5, IL-6, IL-8, IL-13, TNF- $\alpha$ , MCP, MIP-1 $\beta$ , G-CSF, GM-CSF, IFN- $\gamma$  via a cytokine assay.

### 6.4.5.3 Predictive and Prognostic Biomarkers

It is important to identify biomarkers that help to predict and / or evaluate the efficacy of the therapy, in order to achieve the optimal benefit from targeted therapies. No thoroughly validated biomarkers are available to date for anti-PD-1 / PD-L1 and anti-TGF $\beta$  therapies; therefore, this trial plans to evaluate biomarkers from pre-treatment and post-treatment tumor biopsies of primary tissue and blood samples that might be predictive of therapy outcome for all indications. Of note, availability of a tumor sample will be a prerequisite for all subjects.

The following requirements apply to the tissue samples collected during the trial:

**Tissue collection**: Endoscopic biopsies, core needle biopsies, excisional biopsies and surgical specimens are acceptable. Fine needle aspiration biopsies are not acceptable.

Additionally, a mandatory on-treatment biopsy will be performed in cohort A-C prior to cycle 2, day 1 of M7824 administration. A mandatory on-treatment biopsy prior to cycle 1, day 11 and cycle 2, day 1 for cohort B will also be performed. Resected tissue from metastatic resection will serve as the baseline, pretreatment specimen for Cohort D.

**Microbiome sample collection**: Collection of stool samples for microbiome analyses can be done using OMNIgene-Gut kits. OMNIgene-Gut is an all-in-one system for easy self-collections and stabilization of microbial DNA from feces. It allows easily self-collection at home. Samples are rapidly homogenized and stabilized at the point-of-collection and shipped to the laboratory for aliquoting and freezing at -80C prior DNA extraction. This kit allows the collection of high-quality DNA suitable for 16 rRNA microbiome profiling, sequencing and other assays. Buccal swab (buccal smear or cheek swab) will be collected firmly rubbing the entire inner surface of both cheeks for 10 sec each cheek side using a sterile polyester swab and storing in Eppendorf tube at -80°C until DNA extraction and analyses. Tissue processing: The cancer tissues should be fixed in 10% neutral buffered formalin (NBF), paraffin-embedded and routinely processed for histological evaluation. Formalin substitutes are not suited as fixative.

**Tissue storage**: Fresh tumor tissue obtained from subjects for the evaluation of efficacy should be stored in defined cryopreservation medium containing 10% dimethyl sulfoxide [CryoStor® CS10].

**Provision of samples**: 1. priority: tumor-containing formalin fixed, paraffin embedded (FFPE) tissue block; 2. Priority: if the tumor containing FFPE tissue block cannot be provided in total, sections from this block should be provided which are freshly cut, 4  $\mu$ m thick and mounted on positively-charged microscope slides. SuperFrost Plus glass slides are recommended. Preferably, 25 slides should be provided; if not possible a minimum of 10 slides is required. Tumor tissues suitable for biomarker analysis are required. Suitable means that the central laboratory can confirm that the tissue is evaluable (enough viable tumor cells are present).

Sample storage: At the central laboratory the FFPE tissue blocks shall be stored at room temperature and the fresh-frozen tumor slides shall be frozen in sealed containers at -20°C.

A panel of putative markers including molecular, soluble and cellular markers will be analyzed at baseline from archived tumor tissue (or fresh tumor biopsy, preferred when available), and from serum / plasma samples/microbiome to investigate a possible correlation between clinical efficacy and analyzed markers.

The following assessment will be considered:

- CMS classification based on FFPE based RNA expression.
- Level of PD-L1 expression in fresh biopsy by IHC staining. Of note, further techniques to evaluate the expression of PD-L1 and / or marker candidates impacting the targeting or contributing to improve its expression may be also investigated if needed.
- Level of circulating TGFβ.
- Frequency and localization of tumor-infiltrated leukocytes (for example, CD3, CD8, CD4 T-cells, Treg, NK cells, macrophage [M1/2 profile]) by IHC.

- If quantity of tissue permits, genomic characterization of TGFβ signaling components (for example, SMAD4)
- Further exploratory markers related to the MoA) of the drug such as soluble PD-L1 sera level, intratumoral cytokine profile, and auto-antigen proteomic arrays may be explored.
- Further cellular and / or molecular markers specific to the cancer may be also investigated according to the indication.
- Microbiome sequencing analyses of buccal and fecal samples will be conducted.

## 7 Statistics

- 7.1 Sample Size Calculations
- 7.1.1 Cohort A-C

# 7.1.2 The total sample size of this cohort is 15 patients. With this sample size, the half-width of the 95% confidence interval for the estimated response rate will be at most 0.253. Cohort B

For this cohort, the Simon's Optimum two-stage design will be implemented. A historical response rate of 5% and a target response rate of 25% are assumed under the null and the alternative hypotheses, respectively. In the first stage, we will enroll 15 patients; if 1 or fewer achieves a best response of CR/PR, we will stop enrolling patients. Otherwise, we will continue to enroll all 29 patients and the treatment is deemed as promising if there are 4 or more responders out of these 29 patients. The design has a type I error rate of 0.042, a 90% power and a probability of early termination of 82.9% under the null hypothesis. Patient enrollment will be temporarily suspended when the enrollment for the first stage patients has been completed yet not enough responders have been observed to trigger the start of second stage.

## 7.1.3 Cohort D

The total sample size of this cohort is 15 patients. With this sample size, the half-width of the 95% confidence interval for the estimated response rate will be at most 0.253.

### 7.2 Randomization

Not applicable.

## 7.3 Endpoints

## 7.3.1 Primary Endpoints

The primary endpoints are objective response (i.e. CR+PR) according to iRECIST 1.1 criteria for cohorts A-C and B, and clearance of ctDNA for cohort D.

## 7.3.2 Secondary Endpoints

The secondary endpoints to this study are:

- PFS according to iRECIST 1.1 criteria.
- DFS (cohort D)
- OS
- Number, severity, and duration of treatment related AEs according to NCI-CTCAE v4.03

## 7.3.3 Exploratory Endpoints

The exploratory endpoints for this study are:

- Changes in intratumoral immune populations, gene expression and proteomic profiles pre and post-treatment with M7824 where paired biopsies are available
- Changes in circulating immune cell populations and cytokine profiles pre and post-treatment with M7824
- Circulating levels of TGF-β collected from serial plasma samples.

#### 7.4 Analysis sets

The following analysis sets will be defined:

Safety Analysis Set: All subjects who receive at least 1 dose of trial treatment.

### 7.5 Description of Statistical Analyses

#### 7.5.1 General Considerations

All data recorded during the study will be presented in individual data listings performed on the Safety Analysis Set. All data will be evaluated as observed, and no imputation method for missing values will be used. All data will be presented in a descriptive manner. Each cohort will be analyzed separately, and no multiplicity adjustment across cohorts will be performed.

Descriptive statistics will be used to summarize the trial results, that is, statistics for continuous variables may include means, medians, ranges, and appropriate measures of variability. Categorical variables will be summarized by counts and percentages. The uncertainty of estimates will be assessed by confidence intervals. Unless otherwise specified, the calculation of proportions

will be based on the sample size of the analysis set of interest. Counts of missing observations will be included in the denominator and presented as a separate category.

All other statistical analyses will be performed using SAS® Version 9.1.3 or higher, or R, Version 2.10.1 or higher.

## 7.5.2 Analysis of Primary Endpoint

### 7.5.2.1 Response Rate

## 7.5.2.1.1 Cohorts A-C and B

Patient response will be determined using iRECIST 1.1. Unconfirmed responses will not be used in the final analysis. ORR is defined by the number of (PR + CR)/(total number of treatedpatients) in the safety analysis set. For all cohorts, we will estimate the response rate along withthe two-sided exact 95% confidence interval. Also for Cohort B, if the trial continues to the fullenrollment of 29 patients, we will declare M7824 with radiation promising and worthy of furtherinvestigation if there are at least 4 responders out of these 29 patients.

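### Cohort B's planned exact interval takes no account of the two-stage design; a two-stage interval is a cheap, minor improvement

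*Combined protocol and SAP*

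**What the plan says.** Section 7.1.2 sets the Cohort B design. Its two reference rates are given as follows: "A historical response rate of 5% and a target response rate of 25% are assumed under the null and the alternative hypotheses". The stopping rule at stage 1 reads: "In the first stage, we will enroll 15 patients; if 1 or fewer achieves a best response of CR/PR, we will stop enrolling patients". Should the cohort go on to full size, the success rule is that "the treatment is deemed as promising if there are 4 or more responders out of these 29 patients". On error rates the section states: "The design has a type I error rate of 0.042, a 90% power". For stopping at stage 1 it gives "a probability of early termination of 82.9% under the null hypothesis".

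Section 7.5.2.1.1 gives the analysis. The estimate is the raw proportion: "ORR is defined by the number of (PR + CR)/(total number of treatedpatients) in the safety analysis set". The interval, worded identically for every cohort, is a "two-sided exact 95% confidence interval". The rule of at least 4 responders in 29 follows as a separate statement.

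Section 7 names no estimate, interval or p-value that uses the two-stage structure. It does not define which exact interval is meant, and it does not say how the interval relates to the decision rule.

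**The concern.** Single-stage Cohort A-C and two-stage Cohort B share one sentence on the interval. The ordinary binomial interval is exact when the sample size is fixed. In Cohort B the sample size is 15 or 29 depending on the early responses, so that interval's limits no longer come from the probabilities of the results the trial can actually produce.

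Three things follow. The stated 95% level is not guaranteed. The limits may not rise as the result improves. At the smallest successful count, the interval may suggest a different conclusion from the rule. Section 7.5.1 says that uncertainty will be assessed by confidence intervals, so readers will use this one when deciding whether the combination merits further study.

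**Working it through.** **Inputs.** From Section 7.1.2: null rate 0.05, target 0.25, n1 = 15, stop at 1 or fewer, n = 29, promising at 4 or more. X1 is the number of responders among the first 15 patients and X2 the number among the next 14.

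**1. The plan's own figures.**
- Early termination at 5%: 0.95^15 + 15 × 0.05 × 0.95^14 = 0.4633 + 0.3658 = 0.829.
- P(promising) = Σ over x1 ≥ 2 of P(X1 = x1) × P(X2 ≥ 4 − x1). This is 0.0418 at 5% and 0.9001 at 25%.

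All three match the stated 82.9%, 0.042 and 90%. With stage 1 ignored, at least 4 of 29 would give 0.0548 and 0.954.

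**2. Two intervals**, each with error α/2 per side.
- Fixed-sample (Clopper-Pearson), with s responders in n: the lower limit solves P(X ≥ s) = α/2 and the upper solves P(X ≤ s) = α/2.
- Two-stage, with stage 1 stops ranked lowest and then total responders. For a stage 2 result, the lower limit solves P(X1 ≥ 2 and X1 + X2 ≥ s) = α/2. The upper solves P(X1 ≤ 1) + P(X1 ≥ 2 and X1 + X2 ≤ s) = α/2. For a stage 1 stop the limits equal the fixed-sample ones.

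| Result | Responders/n | Fixed 95% | Two-stage 95% | Fixed 90% | Two-stage 90% |
|---|---|---|---|---|---|
| 1/15 (stop) | 6.7% | 0.2–31.9 | 0.2–31.9 | 0.3–27.9 | 0.3–27.9 |
| 2/29 | 6.9% | 0.8–22.8 | 1.7–32.0 | 1.2–20.2 | 2.4–28.1 |
| 4/29 | 13.8% | 3.9–31.7 | 4.2–34.2 | 4.85–28.8 | 5.3–30.9 |
| 5/29 | 17.2% | 5.8–35.8 | 6.1–36.9 | 7.0–32.9 | 7.3–33.8 |

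**3. Order of the limits.** The fixed-sample 95% upper limit falls from 31.9% at 1/15 to 22.8% at 2/29. The result that passed stage 1 is the one that appears to rule out the 25% target. The two-stage limits rise, from 31.9% to 32.0%.

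**4. Coverage.** This is the sum, over all possible results, of the probability of each result whose 95% interval contains the true rate.

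| True rate | 5% | 10% | 15% | 20% | 25% | 30% |
|---|---|---|---|---|---|---|
| Fixed-sample coverage | 98.8% | 97.9% | 97.8% | 98.0% | 96.8% | 97.8% |

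Just above 31.9%, five results have upper limits below the true rate: 0/15, 1/15, 2/29, 3/29 and 4/29. At 32% their probabilities are 0.0031 + 0.0217 + 0.0003 + 0.0028 + 0.0118 = 0.0397, against a nominal 0.025. The lower-side error there is 0.0215, so coverage is 1 − 0.0397 − 0.0215 = 93.9%. On a grid of true rates from 1% to 60% in steps of 0.05 points, coverage is below 95% only from 31.95% to 32.5%, and upper-side error peaks at 4.0%. The two-stage interval's lowest coverage on that grid is 95.2%.

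**5. The success threshold.** At 4/29 the one-sided p-value against 5% is 0.0418 under the two-stage design and 0.0548 under a fixed sample. Only the first is below 0.05, so only the two-stage 90% interval excludes 5%. Both exceed 0.025, so both 95% intervals include 5%. From 5/29 upward, every interval excludes 5%. The probability of exactly 4/29 is 3.0% at a true 5% (0.0300/0.0418 = 72% of promising results) and 5.1% at a true 25% (0.0508/0.9001 = 5.6% of them).

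**6. Point estimate.** The bias of responders/n is −0.8, −1.6, −1.6, −1.2 and −0.8 points at true rates of 5, 10, 15, 20 and 25%. The uniformly minimum variance unbiased estimate (UMVUE) has no bias; at 4/29 it is 16.8% against 13.8%. Root mean squared error in points, responders/n against UMVUE, is 4.4 v 5.5 at 5%, 6.4 v 7.2 at 10%, 8.0 v 8.0 at 15% and 8.8 v 8.5 at 20%.

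**The case against.** The best defence is that nothing in the trial turns on this interval. Sections 7.1.2 and 7.5.2.1.1 base the conclusion on the responder count, and Section 7.5.1 describes the analyses as descriptive. The design's error rates reproduce. The fixed-sample interval is conservative at most rates, and the shortfall lies in a band about half a point wide, above the 25% target. The 2/29 result has probability 0.28% at a true 25%, and the treatment is not declared promising there under either method. The two-stage upper limit at 2/29 is itself hardly different from that at 1/15, despite 14 more patients. All of this stands, and it keeps the point minor.

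A reader might infer something stronger: that ignoring the two stages makes the reported interval contradict the decision rule. The documents do not support that. The planned level is 95%, and at 4/29 the two-stage 95% interval (4.2% to 34.2%) contains 5% just as the fixed-sample one does. The main cause is the level: a two-sided 95% interval tests at 2.5% on each side, while the rule has a one-sided error of 4.2%. Agreement needs both the 90% level and the two-stage method. The mismatch arises at one successful count only, and no passage makes the decision depend on the interval.

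A reader might also infer that responders/n should be replaced. A bias of at most 1.6 points, with higher error from the UMVUE at low rates, does not justify that.

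**Conclusion.** The concern holds in a limited form. As most naturally read, the planned interval for Cohort B is not an exact 95% interval under the two-stage design. Its coverage ranges from 98.8% down to 93.9% over the rates examined, its upper limits are out of order between 1/15 and 2/29, and its 90% version does not match the rule at 4/29. No decision, error rate or sample size changes. Severity is minor, and the change is a cheap improvement.

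The conclusion rests on four assumptions: that exact means Clopper-Pearson, which the plan does not say; that the cohort ends with exactly 15 or 29 treated patients; that the stage 1 rule is followed; and that stopping for toxicity under Section 7.6 is left out of the sample space.

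**What to change.** In Section 7.5.2.1.1, add for Cohort B that the exact interval is computed on the two-stage sample space with stage-wise ordering. Report it at 95% and also at 90%, the level that corresponds to a one-sided 5% test. State that the go decision rests on the responder count and not on the interval.

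Keep responders over treated patients as the reported response rate. The UMVUE may be shown beside it as a supplement. Keep the fixed-sample interval for Cohorts A-C and D, and name it there.

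The cost is one or two sentences and a few lines of code. The downside is a less familiar interval that is somewhat wider at low counts: at 4/29 the 95% interval spans 30.0 points (34.2 − 4.2) against 27.8 (31.7 − 3.9).
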